### Patient Diary

Patient Number: I\_I\_I\_I\_I\_I\_I\_I\_I\_I

Record from: \_\_\_\_\_ to: \_\_\_\_\_

Date of your next visit: \_\_\_\_\_

**EMERGENCY CONTACT:**

---

Call your study team immediately if you are experiencing any new symptoms (diarrhea, vomiting, etc.).

**TAKE TABLETS AS PRESCRIBED BY YOUR STUDY DOCTOR. PLEASE BRING ORIGINAL STUDY MEDICATION BOTTLES WITH YOU TO EACH STUDY VISIT**

Please complete the diary every day and bring it with you to the next scheduled visit as instructed.

## COMPLETION GUIDELINES

1. Enter the study drug that you are taking each day under the column “Name of Drug” and complete corresponding dose and # of tablets taken.
2. Make sure to enter the amount of loperamide you are taking as well (see example on table below).
3. If you experience diarrhea, enter # of stools per day.

Date dd/mm/yy	Name of Drug	Time Taken	Dose Taken	# of Tablets per Day	# of Stools per Day	Comments on missed or reduced doses for Study Medication(s), any additional anti- diarrheal medication, and any symptoms (i.e. Diarrhea, Vomiting, Pain)
05/Sep/12 (Day 1)	Neratinib		240 mg	6		
05/Sep/12	Loperamide		4 mg	2	0	
06/Sep/12	Neratinib		240 mg	6	3	(+) diarrhea

## Appendix N: Registration Coversheet

**COH IRB (Insert Please): PHASE II STUDY OF NERATINIB IN PATIENTS 60 AND  
OLDER WITH HER2 POSITIVE LOCALLY ADVANCED OR METASTATIC BREAST  
CANCER**

## Appendix O: Stool Collection Procedure

### STOOL COLLECTION KIT GENERAL INSTRUCTIONS

As a part of your participation in the current study, we have some specific instructions related to collection of stool. Please abide by these instructions, as they are essential for the proper conduct of the study.

You are being asked to collect samples at the following times:

- 7 days prior to start of neratinib
- C1Day 15 (+/- 3 days), C2Day1 (+/- 3 days), C2Day15 (+/-3 days), C3Day1 (+/- 3 days).

If you have any questions about sample collection, please call this number:

### USING THE STOOL COLLECTION KIT

#### Before you begin, review the following:

- a. Make sure you have a *collection hat* and collection tube.
- b. Make sure you are able to deliver the sample to City of Hope within 1 week.

STEP ONE: Please place the collection hat around the rim of your toilet seat for stool collection.
  
<small>Do not use the toilet seat to collect the stool.</small>
	

STEP TWO: Unscrew the collection tube cap and use the spoon to scoop one spoonful of feces (about the size of a quarter) from a sample. Place the sample in the collection tube. Tighten the cap and shake to mix the contents thoroughly (invert 10 times) to create a suspension.
 
Note: Some fecal material may be difficult to re-suspend. As long as the material is suspended, the sample is stabilized. Foaming/frothing during shaking is normal.
	 
<small>Scoop a portion of the stool sample into the DNA/RNA Shield™ Fecal Collection Tube</small>

**STEP THREE:** Wash hands well, and write today's date on the label.

**STEP FOUR:** Place the plastic tube in the bag, and seal the back using the adhesive tape already present on the bag.

**STEP FIVE:** Bring the sample to your City of Hope appointment.

**THANK YOU FOR YOUR  
PARTICIPATION!**

## Appendix P: Diet and Stool Frequency Log

**DIET and STOOL FREQUENCY LOG - GENERAL INSTRUCTIONS**

As a part of your participation in the current study, we are requesting that you complete a study log every day.

General pointers:

- When you come to the clinic, bring your logs with you.
- Each page has room for seven days – one row should be completed for each day.
- Please **avoid any intake of yogurt, yogurt-containing foods, or other bacteria-fortified foods.**

Example of how the top part of the log will look:

- A study team member will complete the information in this box before you leave the clinic.

COMPLETED BY STUDY TEAM	Participant Initials: JSM	Participant Research Number: 1001	Group: A
-------------------------	----------------------------------	--	-----------------

Example of how the information you enter might look:

- You or someone close to can complete the log for you, so long as the information is correct.
- List all prescription and non-prescription medications.
- The person who completes that day's entry should write his or her initials in the last column.

Day and Date	General description of food I ate:	Did I eat yogurt or take probiotics?	How was my stool frequency?	Was a stool sample collected?	Medications taken	Initials of person filling information
	Eggs, toast, juice Ham sandwich, coke, potato chips Steak, mashed potatoes, wine	 Yes  No	 Seems like baseline  1-3 stools more than baseline  4-6 stools more than normal  7 or more than baseline, or incontinence   Seems like baseline	 Yes  No	Vitamin C, Lipitor	JSM

Example of the signature line:

- When you hand over the document to the study team, they will ask to sign and date at the bottom of each log if you agree that the information is complete and correct.

At the time of handing over the document -- Participant Signature: Joseph Black Smith Date 12/18/2002

COMPLETED BY STUDY TEAM	Participant Initials:	Participant Research Number:
-------------------------	-----------------------	------------------------------

Day and Date	General description of food I ate:	Did I eat yogurt or take probiotics?	How was my stool frequency?	Was a stool sample collected?	Medications taken	Initials of person filling information
	Eggs, toast, juice Ham sandwich, coke, potato chips Steak, mashed potatoes, wine	 Yes  No	 Seems like baseline  1-3 stools more than baseline  4-6 stools more than normal  7 or more than baseline, or incontinence	 Yes  No	Vitamin C, Lipitor	LBC
		 Yes  No	 Seems like baseline  1-3 stools more than baseline  4-6 stools more than normal  7 or more than baseline, or incontinence	 Yes  No		
		 Yes  No	 Seems like baseline  1-3 stools more than baseline  4-6 stools more than normal  7 or more than baseline, or incontinence	 Yes  No		
		 Yes  No	 Seems like baseline  1-3 stools more than baseline  4-6 stools more than normal  7 or more than baseline, or incontinence	 Yes  No		
		 Yes  No	 Seems like baseline  1-3 stools more than baseline  4-6 stools more than normal  7 or more than baseline, or incontinence	 Yes  No		
		 Yes  No	 Seems like baseline  1-3 stools more than baseline  4-6 stools more than normal  7 or more than baseline, or incontinence	 Yes  No		
		 Yes  No	 Seems like baseline  1-3 stools more than baseline  4-6 stools more than normal  7 or more than baseline, or incontinence	 Yes  No		

		 Yes	 Seems like baseline  1-3 stools more than baseline  4-6 stools more than normal  7 or more than baseline, or incontinence	 Yes		
		 No		 No		

At the time of handing over the document -- Participant Signature: \_\_\_\_\_ Date .

## **Appendix Q: At Home Sample Collection Kit Contents**

---

Contents of each kit to be provided to participants for at home collection:

- Copy of Appendix O: Instructions for Stool Specimen Collection
- Stool collection hat
- Specimen tube with label attached
  - **Label should have participant identifier added;** the participant will be asked to add the date himself/herself.
- Plastic sealable bag

## Appendix R: Checklist for study nurses, including documentation of patient's primary language for Geriatric Assessment

Patient's name and MRN \_\_\_\_\_

Patient's primary language \_\_\_\_\_

	Pre-study (up to 28 days prior to enrolling) i	C1D1 (28 day cycle)	C1D8 ( $\pm$ 1 day)	C1D15 ( $\pm$ 1 day)	C2D1 ( $\pm$ 3 days)	C2D15 ( $\pm$ 3 days)	C3D1 ( $\pm$ 3 days)	C4D1 ( $\pm$ 3 days)	C5D1 ( $\pm$ 3 days)	C6D1 ( $\pm$ 3 days)	Every cycle thereafter ( $\pm$ 3 days)	Every 3 cycles ( $\pm$ 7 days)	Off treatment h
Diarrhea Checklist		 											
Nurse brief toxicity evaluation													
Adherence evaluation (pill count, diaries) ( $\pm$ 1 week)													
Tumor measurements using CT or PET-CT ( $\pm$ 1 week)	 d											 e	 f
Geriatric Assessment Survey ( $\pm$ 1 week)													 g

d: Baseline assessment may be done up to 30 days prior to study enrollment.

e: Tumor measurements are repeated every 3 cycles  $\pm$  1 wk until patient comes off study. Documentation (radiologic or clinical) must be provided for patients removed from study for progressive disease.

f: Off-study radiologic evaluation will only be done if clinically indicated.

g: Geriatric assessment will be performed at baseline prior to study, after 3 cycles and at the end of study. Geriatric assessment will be repeated off study ONLY if it had not been administered within the previous month. If patient's native language is not covered by the current language forms, geriatric assessment form can be omitted with clear documentation.

h: Patients will be followed for 30 days following discontinuation of therapy in order to capture toxicity attributable to therapy.

i: Chart review data must be within 28 days to determine if patient meets study criteria. Once patient meets study criteria, then all criteria must be within window specified in protocol from Day 1 as indicated in column one in the schema above.

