### 7.6.1 Required Concomitant Treatment

#### 7.6.1.1 Loperamide Antidiarrheal Therapy

Diarrhea is the major dose-limiting toxicity of neratinib with onset typically occurring early in the course of treatment (during the first few weeks). Primary prophylactic use of antidiarrheal medication is **mandatory** for all enrolled patients in the neratinib study.

Loperamide is the recommended standard therapy to treat diarrhea in this study. If alternative antidiarrheal medication is proposed, this should be discussed with the PI and the reason documented in the source documents. Second-line antidiarrheal treatments and adjunctive

therapies (i.e., octreotide [SANDOSTATIN®]) (or equivalent as approved by the PI) are also recommended for use when appropriate.

All patients are required to receive intensive diarrhea prophylaxis:

- For the first 14 days, loperamide 4 mg (2 tablets/capsules) will be self-administered orally by patients 3 times a day (total 12 mg a day). The initial dose of loperamide 4 mg will be self-administered orally with the first dose of neratinib.
- After the first 14 days, loperamide 4 mg (2 tablets/capsules) will be self-administered orally twice a day (total 8 mg a day) through the first cycle of therapy (Day 28) from start of neratinib dosing.
- Thereafter, loperamide will be administered as needed (not to exceed 16 mg per day). The goal is to titrate to 1-2 bowel movements a day. Recommended loperamide dosing is listed below in **Table 5**.

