Loperamide will be dispensed directly by the site on or before Cycle 1/Day 1 with neratinib. It is very important to initiate treatment with loperamide concomitantly with the first dose of neratinib to minimize occurrence and severity of diarrhea.

#### 7.6.1.2 Prophylactic dosing instructions for Cycle 1

- Inform patients that they will experience diarrhea while taking neratinib.  
Administer loperamide:
  - For the first 14 days, loperamide 4 mg (2 tablets/capsules) will be self-administered orally by patients three times a day (total 12 mg a day). The initial dose of loperamide 4 mg will be self-administered orally with the first dose of neratinib.
  - After the first 14 days, loperamide 4 mg (2 tablets/capsules) will be self-administered orally twice a day (total 8 mg a day) through the first cycle of therapy (Day 28) from start of neratinib dosing.

- Thereafter, loperamide will be administered as needed (not to exceed 16 mg per day).
- The goal is to maintain the loperamide prophylaxis dose with a goal of titrating to 1-2 bowel movements a day.
- For patients who develop diarrhea during Cycles 1, loperamide should be increased up to a maximum of 16 mg a day.
- For patients with persistent Grade 1 diarrhea (<4 stools per day above baseline) on loperamide, Lomotil® (diphenoxylate hydrochloride and atropine sulfate) 1 tablet (2.5 mg) every 6 to 8 hours may be added (or equivalent as approved by PI).
- For Grade 2 diarrhea during Cycle 1 (4 to 6 stools per day above baseline, despite intensive loperamide): add lomotil 2.5mg every 6 to 8 hours, consider adding octreotide (short-acting) 150 µg subcutaneous [SC] injection 3 times a day, or after initial dose of short-acting octreotide, if well tolerated, a single dose of octreotide LAR 20 mg by intramuscular injection (equivalent medication may be used with approval of the Investigator). For persisting Grade 2 diarrhea during Cycle 1 despite the use of both imodium and lomotil: add octreotide as directed above.
- For Grade 3 diarrhea management during Cycle1: please refer to Table 7 and 8 for dose hold and reduction.
- For Grade 4 diarrhea management during Cycle 1: recommend permanently discontinue neratinib

The sites must contact the patient by phone at 1 day, 2 days, and 3 days after the first dose of neratinib:

- To inquire about any diarrhea and about potential AEs;

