#### 7.7 Laboratory Studies/Monitoring Studies

##### **7.7.1 Required Clinical, Laboratory and Disease Evaluation at Baseline**

Complete blood count and differential, comprehensive metabolic panel (including sodium, potassium, chloride, bicarbonate, blood urea nitrogen, creatinine, glucose, calcium, ALT, AST, alkaline phosphatase, total bilirubin, total protein, and albumin), must be performed within 14 days of enrolling on trial.

A full history and physical exam including demographics, medical history, concurrent medications, vital signs, height measurement, weight measurement, and performance status analysis must be done within one week of enrolling on trial.

Radiologic evaluation including computed tomography (CT) of the chest, abdomen, and pelvis; or combined PET-CT with a diagnostic CT component, must have been performed within 30 days of study enrollment. If measurable disease is present, tumor measurements must be performed and reported from this scan. Central review is not required for treatment decisions in individual subjects.

The patient must complete a Geriatric Assessment prior to starting therapy (see Appendix I). If patient's native language was not covered by the current language forms, Geriatric assessment form can be omitted with clear documentation.

Cardiac imaging (either by echocardiogram or MUGA scan) with a reported left ventricular ejection fraction must be obtained within 30 days of study enrollment. Regardless of where the baseline evaluation is performed, future cardiac evaluation must be performed using only the

same modality as the baseline evaluation. A baseline EKG before starting treatment is also required.

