#### 7.7.3.3 *Geriatric Assessment*

Geriatric assessment surveys will be administered at baseline( $+$ / $-$  7 days), after every four cycles, cycle 4 day 1( $+$ / $-$  7 days), cycle 7 day 1( $+$ / $-$  7 days) and at the end of the study ( $+$ / $-$  7 days) if not performed in the previous month (see Appendix I for Geriatric Assessment Survey). If patient's native language was not covered by the current language forms, Geriatric assessment form can be omitted with clear documentation.

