- g: Geriatric assessment will be performed at baseline prior to study, after 3 cycles ( $\pm$ 7 days) and at end of study ( $\pm$ 7 days). Geriatric assessment will be repeated off study ONLY if it had not been administered within the previous month. If patient's native language was not covered by the current language forms, Geriatric assessment form can be omitted with clear documentation.
- h: Patients will be followed for 30 days following discontinuation of therapy in order to capture toxicity attributable to therapy.
- i. Chart review data must be within 28 days to determine if patient meets study criteria. Once patient meets study criteria, then all criteria must be within window specified in protocol from Day 1 as indicated in column one in the schema above.
- j: Pharmacokinetics samples will be collected at the following time points: Cycle 1 Day 15 pre-dose ( $\pm$  20 minutes) and 6 hours post-dose ( $\pm$  60 minutes); pre-dose ( $\pm$  20 minutes) on Cycle 3 Day 1 and Cycle 4 Day 1. All pre-dose samples should be collected within 30 minutes before the daily dose in 10 ml purple-top tube.
- k: Peripheral blood correlates for inflammatory marker measurement (IL-6, CRP and D-dimer) and ctDNA will be collected in 10 ml purple-top tube at baseline, after 3 cycles (Cycle 4 Day 1  $\pm$  7days), and at end of study ( $\pm$ 7days) when patient receives geriatric assessment.
- L: An "Optimal Management of Diarrhea Checklist" will be reviewed and signed by study investigator or study nurse on Cycle 1 Day1. The study team will call patients at 1day, 2 days and 3 days after first dose of neratinib to assess tolerance.
- m. Stool samples must be collected within 7 days prior to start of neratinib, C1Day 15 (+/-3 days), C2Day1 (+/-3 days), C2Day15 (+/-3 days), C3Day1 (+/-3 days).

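### The rule for skipping the off-study geriatric assessment does not exempt the baseline one, so a few patients who stop within about a month may have no post-baseline assessment

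*Combined protocol and SAP*

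**What the plan says.** Appendix R, footnote g, sets the time points: "Geriatric assessment will be performed at baseline prior to study, after 3 cycles and at the end of study". The next sentence limits the last of them: "Geriatric assessment will be repeated off study ONLY if it had not been administered within the previous month". The same footnote stands under the Experimental Design Schema at the front of the protocol and under section 12.0. Section 7.7.3.3 makes the end-of-study assessment conditional in the same way, "if not performed in the previous month".

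On baseline timing, section 7.7.1 states "The patient must complete a Geriatric Assessment prior to starting therapy", section 7.7.3.3 gives a 7-day window around baseline, and the schedule column is headed "Pre-study (up to 28 days prior to enrolling", closed by a bracket. Geriatric assessment score is a listed secondary endpoint (section 3.2).

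Footnote k in section 12.0 times the end-of-study blood sample to the occasion "when patient receives geriatric assessment".

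**The concern.** The purpose of the skip rule is plain: a long questionnaire should not be repeated within a few weeks. That works when the recent assessment is the one at Cycle 4 Day 1, because that value already reflects treatment. It does not work when the recent assessment is the baseline one. The patient then leaves with a pre-treatment value only.

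The patients concerned are not a random subset. Section 7.6.1.1 says "Diarrhea is the major dose-limiting toxicity of neratinib with onset typically occurring early in the course of treatment", and section 7.6.1.2 says "For Grade 4 diarrhea management during Cycle 1: recommend permanently discontinue neratinib". Table 8 also recommends discontinuation for prolonged or complicated grade 3 diarrhea, with an option to hold and resume. Stopping for early toxicity is therefore a documented route into the group whose follow-up assessment is skipped. Withdrawal of consent and symptomatic progression are others. At stake is any summary of geriatric assessment score after the start of treatment: it would leave out some of the patients who tolerated the drug worst, and the missing values cannot be recovered later.

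**Working it through.** The plan gives no figure on this point, so there is none to reproduce. The check is of wording, dates and counts.

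**1. Does the rule count baseline?** Footnote g first lists three assessments, baseline among them, and then says the assessment is not repeated if given in the previous month. No exemption is stated in any of the four places. Counting baseline is the literal reading, although the text does not say so expressly.

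**2. Is there another assessment to fall back on?** The schedule tables show none between baseline and Cycle 4 Day 1, which is Day 3 × 28 + 1 = 85. Section 7.7.3.3 adds Cycle 7 Day 1 but nothing earlier. A patient caught by the rule has no later value.

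**3. How long is the window?** Let the baseline assessment be done d days before Day 1, and let a month be m = 28 to 31 days (an assumption, as the plan does not define it). The off-study assessment is skipped if it falls due by about Day m − d, to within a day depending on how Day 1 is counted.

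| Baseline, days before Day 1 (d) | Last day skipped (m = 28 to 31) |
|---|---|
| 0 | Day 28 to 31 |
| 7 | Day 21 to 24 |
| 14 | Day 14 to 17 |
| 21 | Day 7 to 10 |
| 28 | Day 0 to 3 |

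Under the 7-day window of section 7.7.3.3 the rule is active until about Day 21 to 31. If the full 28 days of the pre-study column are used, it hardly operates.

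**4. When does the off-study assessment fall due?** If it is done when treatment stops, step 3 applies. If it is done at the end of the 30-day toxicity follow-up, the earliest possible date is 30 days after a single dose on Day 1, that is Day 31. The baseline assessment then cancels it at most in an edge case (same-day baseline, one dose, longest reading of a month). The documents point both ways. The footnote sits in the off-treatment column and Appendix I labels the time point as end of treatment, while footnote g and Appendix H speak of end of study.

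**5. How many patients?** The documents give no first-month discontinuation rate. Section 1.4.5.4 gives pooled any-time rates: 6.1% of subjects stopped for diarrhea, and 2.8% for grade 3 diarrhea. I add 10% as an assumed upper value to allow for other reasons and an older population. With n = 40, the expected count is 40 × p and the chance of at least one is 1 − (1 − p)^40.

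| p | Expected patients | Chance of at least one |
|---|---|---|
| 2.8% | 1.1 | 0.68 |
| 6.1% | 2.4 | 0.92 |
| 10% | 4.0 | 0.99 |

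**6. How far could a descriptive summary shift?** If a share e is missing and declines at rate a while the rest decline at rate b, the observed rate is too low by e × (a − b). With e = 6.1% and purely illustrative rates of 60% against 20%, this is 0.061 × 0.40 = 2.4 percentage points. With 50% against 30% it is 0.061 × 0.20 = 1.2 points. Section 15.1 puts the widest 95% half-width for a proportion in 40 patients at 0.16.

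**The case against.** Most of the case on the other side stands.

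- **Toxicity and the primary endpoint.** A reader might infer that follow-up is lost for the worst early toxicity. The documents do not support that. Adverse events are evaluated at every visit and off treatment, and patients are followed for 30 days after stopping, whatever happens to the geriatric assessment.
- **Blood samples.** A reader might infer from footnote k that skipping the questionnaire also cancels the end-of-study IL-6, CRP, D-dimer and ctDNA draw. The blood row has its own off-treatment mark without the skip footnote, and the synopsis calls the biomarker samples mandatory at the end of study. Footnote k reads naturally as timing.
- **Understated decline.** A reader might say the trial will underestimate geriatric decline. No decline or change-from-baseline analysis is specified. The objective (section 2.2) is prediction of toxicity, and section 15.3 uses geriatric factors as predictors. The baseline assessment serves for that, and early stoppers have it, apart from the language exception.
- **Few patients stop this early.** Treatment may be held for up to 4 weeks (section 8.0), and several grade 3 events lead to hold and reduction (Tables 7 and 8). Section 10.2.1 reports no grade 4 diarrhea under loperamide prophylaxis. Many patients with early toxicity would still be on study at Day 31.
- **Burden.** Appendix H is long, and not repeating it within a month is a reasonable choice for older patients.

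None of this answers the narrow point. The rule as written can leave a patient with no assessment after the start of treatment, and the burden argument has less force when the only earlier value predates the drug.

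**Conclusion.** The point holds in a limited form. Read literally, footnote g and section 7.7.3.3 let a recent baseline assessment cancel the off-study one. A patient assessed 0 to 7 days before Day 1 who goes off treatment by about Day 21 to 31 would then have no post-baseline geriatric assessment. The consequence is confined to descriptive follow-up data on one secondary endpoint, in about 1 to 4 of 40 patients.

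This rests on three assumptions: that the baseline assessment counts under the rule, that the off-study assessment is due at or near the end of treatment, and that an any-time discontinuation rate is a fair guide to first-month stopping. If the second fails, or baseline is done about 28 days early, the gap almost disappears. The missing data are probably informative, but the documents give no basis for stating the size of any bias. This is a minor, inexpensive clarification.

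**What to change.** In footnote g (front schema, section 12.0, Appendix R) and in section 7.7.3.3, state that the off-treatment geriatric assessment may be skipped only if a post-baseline assessment was done within the previous month. A patient with no post-baseline assessment then has one at that visit, subject to the existing language exception. In the same places, define when the off-study assessment falls due: at the end of treatment or after the 30-day follow-up.

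Footnote k needs at most a clarifying phrase that the end-of-study blood is drawn whether or not the questionnaire is repeated, as the schedule already implies. While section 7.7.3.3 is open, reconcile its time points (every four cycles, Cycle 4 Day 1, Cycle 7 Day 1) with the schedule tables, which show baseline, after 3 cycles and end of study.

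The cost is wording in four places and roughly 1 to 4 extra questionnaires of a kind already planned. The drawback is that they fall on patients who have just stopped treatment, some of them unwell.
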